5. DATA MANAGEMENT

Personal data collected during the trial will be handled and stored in accordance with the 1998 Data Protection Act.

The Case Report Forms will be designed by the TC in conjunction with the TMG. All electronic patient-identifiable information will be held on a secure, password-protected database accessible only to authorised personnel. Paper forms with patient-identifiable information will be held in secure, locked filing cabinets within a restricted area of Warwick Medical School. Participants will be identified by a code number only. Direct access to source data/documents will be required for trial-related monitoring. All paper and electronic data will be retained for at least ten years after completion of the trial.

5.1 Database

The database will be developed by the Programming Team at WCTU and all specifications (i.e. database variables, validation checks, screens) will be agreed between the programmer and appropriate trial staff.

5.2 Data storage

All essential documentation and trial records will be stored by WCTU in conformance with the applicable regulatory requirements and access to stored information will be restricted to authorised personnel.

5.3 Archiving

Trial documentation and data will be archived for at least ten years after completion of the trial.

6. STATISTICAL ANALYSIS

6.1 Power and sample size

There is no consensus on a minimum clinically important difference (MCID) regarding the VISA-A score. However, previous studies propose that the MCID lies between 10 and 12 points and that this is in keeping with comparable patient reported outcomes in musculoskeletal medicine. We have therefore chosen an MCID of 12 points.

From our pilot data, the VISA-A data were observed to be approximately normally distributed with a standard deviation of 26. If the true difference between the experimental and control treatment group means is 12, a sample of 100 patients in each group will be required to reject the null hypothesis (population means of the experimental and control groups are equal) with probability 0.9 (90% power). This equates to an effect size of 0.46 (12/26), which we would consider to be moderate. The Type I error rate (significance level) associated with this test is 5%. Allowing approximately 20% loss to follow-up, this amounts to 240 patients in total

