6.2 Statistical Analysis Plan

It seems likely that some data may not be available due to voluntary withdrawal of participants, lack of completion of individual data items or general loss to follow-up. Where possible the reasons for data 'missingness' will be ascertained and reported. Although missing data is not expected to be a problem for this study, the nature and pattern of the missingness will be carefully considered, including in particular whether data can be treated as missing completely at random or missing at random. If judged appropriate, missing data will be imputed using the multiple imputation facilities (mice package) available in R (<http://www.r-project.org/>). The resulting imputed datasets will be analysed and reported, together with appropriate sensitivity analyses. Any imputation methods used for scores and other derived variables will be carefully considered and justified. Reasons for ineligibility, non-compliance, withdrawal or other protocol violations will be stated and any patterns summarized. More formal analysis, for example using logistic regression with 'protocol violation' as a response, may also be appropriate and aid interpretation.

Standard statistical summaries (e.g. medians and ranges or means and variances, dependent on the assumed distribution of the outcome) and graphical plots showing correlations will be presented for the primary outcome measure and all secondary outcome measures. Baseline data will be summarised to check comparability between treatment arms, and to highlight any characteristic differences between those individuals in the study, those ineligible, and those eligible but withholding consent.

The main analysis will investigate differences in the primary outcome measure, the VISA A at six months after treatment, between the two treatment groups on an intention-to-treat basis. In addition, early functional status will also be assessed and reported at three months. The differences between treatment groups will be assessed using a Student t-test, based on a normal approximation for the VISA A score at 6 months, and at other occasions. Tests will be two-sided and considered to provide evidence for a significant difference if p-values are less than 0.05 (5% significance level). Estimates of treatment effects will be presented with 95% confidence intervals.

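### Section 6.1 reaches 240 by adding 20% to the 200 evaluable patients; allowing for about 20% loss gives 250, and 240 leaves 192 patients and about 89% power (a minor error)

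*Protocol*

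**What the plan says.** Protocol section 6.1 sizes the trial on the six-month VISA-A score. The condition is "If the true difference between the experimental and control treatment group means is 12", and the pilot scores were "approximately normally distributed with a standard deviation of 26". For 90% power at the 5% level, the section says that "a sample of 100 patients in each group will be required to reject the null hypothesis". It then moves from evaluable to randomised patients in one sentence: "Allowing approximately 20% loss to follow-up, this amounts to 240 patients in total".

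Three other places bear on this. Section 2.1 fixes 240 as the number to be randomised, in a 1:1 ratio. Section 2.6.2.1 says that participants who withdraw are not replaced. Section 6.2 compares the groups with a Student t-test and adds that "Tests will be two-sided".

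**The concern.** The figure of 100 per group is a requirement for patients with outcome data. The allowance for loss should ensure that about 200 such patients remain once the expected share of randomised patients has dropped out. The figure 240 is exactly 200 plus one fifth of 200, which suggests that the 20% was applied to the evaluable number and not to the randomised number. The two calculations differ: taking 20% off 240 does not return 200.

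What is at stake is whether section 6.1 agrees with itself. A reader of the section would conclude that the trial keeps 90% power if one patient in five is lost, and on the section's own inputs it does not. Sample-size statements are usually carried into the trial report, so the mismatch is worth correcting at source. The validity of the trial is not in question.

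**Working it through.** **Inputs, all from the protocol.** Difference 12, SD 26, power 90%, significance level 5%, 100 evaluable per group, loss of approximately 20% and total 240 (section 6.1); two-sided Student t-test (section 6.2); 1:1 allocation and 240 randomised (section 2.1); withdrawals not replaced (section 2.6.2.1).

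**Step 1: reproduce the evaluable number.**
- Standardised difference: 12/26 = 0.4615, which the protocol rounds to 0.46.
- Normal approximation: n per arm = 2 x (26/12)² x (1.960 + 1.282)² = 2 x 4.694 x 10.507 = 98.7, so 99.
- Two-sample t-test (noncentral t): 99.6, so 100.
- Power at 100 per arm: 90.1% by the t-test, 90.4% by the normal approximation.

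The protocol's 100 per group is right. It has almost no slack, since 99 per arm gives 89.8% by the t-test.

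**Step 2: reproduce the inflation.** With E evaluable patients needed and a fraction d of randomised patients lost, the number to randomise is N = E/(1 − d).
- Correct: 200/(1 − 0.20) = 250, or 125 per arm.
- The protocol's figure is recovered by E x (1 + d) = 200 x 1.20 = 240.
- Starting from 198 evaluable (99 per arm, normal approximation) gives 198/0.80 = 247.5, so 248. That choice does not explain 240 either.

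**Step 3: what 240 delivers.**
- Evaluable at 20% loss: 240 x 0.80 = 192, or 96 per arm.
- Shortfall: 200 − 192 = 8 evaluable patients, or 250 − 240 = 10 randomised patients.
- Loss at which 200 remain: 1 − 200/240 = 16.7%.

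**Step 4: power with 240 randomised (difference 12, SD 26, two-sided 5%).**

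| Loss | Evaluable | Power, t-test | Power, normal |
|---|---|---|---|
| 15% | 204 | 90.7% | 90.9% |
| 16.7% | 200 | 90.1% | 90.4% |
| 18% | 196.8 | 89.6% | 89.9% |
| 19% | 194.4 | 89.3% | 89.6% |
| 20% | 192 | 88.9% | 89.2% |

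At 20% loss, power is 90.1 − 88.9 = 1.2 points below the power at 100 per arm, and 1.1 points below the nominal 90%.

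**Step 5: does the recruitment timetable cover the gap?** Section 7.5 projects 243.6 recruits by the last recruiting month. At 20% loss that leaves 243.6 x 0.80 = 194.9, still below 200.

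**The case against.** The strongest defence is the protocol's wording. It says approximately 20%, and 16.7% might be thought close enough. At 18% loss the power is still 89.6%, which most readers would round to 90%. This part stands as mitigation: the error should not be described as if the protocol had planned on exactly 20%. It does not remove the error. A loss of 16.7% would ordinarily be called about 17%, and the exact match to 200 x 1.2 points to the wrong formula more than to rounding.

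It is also fair to say that the protocol ties 90% power to 100 patients per group, and that statement is correct. Only the step to 240 is wrong.

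The effect is also small beside the uncertainty in the inputs. With an SD of 26.5 in place of 26, power at 100 per arm is 89.0%, much the same fall. Section 6.2 mentions a pilot sample of twenty. If the SD was estimated from those twenty (an assumption, with 18 to 19 degrees of freedom), its 95% interval runs from about 20 to 38. This stands, and it is why the point is minor.

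Finally, section 2.6.2.1 allows outcome completion by telephone or in clinic, with text reminders, and section 6.2 allows multiple imputation if judged appropriate. These may limit loss or its effect in practice. They do not make the sentence in section 6.1 correct.

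**Conclusion.** The inflation in section 6.1 is wrong as written. On the protocol's own inputs, about 20% loss calls for 250 randomised. The stated 240 leaves 192 evaluable patients and 88.9% power at 20% loss, and holds 200 evaluable only up to 16.7% loss. The error is minor, at about one percentage point of power. The figures assume equal loss in the two arms, an SD of 26, a true difference of 12, and an unadjusted two-sided t-test on observed six-month scores.

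A reader might infer three stronger things that the document does not support:

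- **That the trial is materially underpowered or must be enlarged.** A fall of about one point does not justify that.
- **That adjusting for baseline VISA-A would recover the lost power, so nothing is lost.** Section 6.2 bases the comparison on unadjusted t-tests. The adjustments it names are for age, gender, recruiting centre and bilateral presentation. Baseline VISA-A is collected but is not named as a covariate, so this protocol gives no basis for relying on it.
- **That the trial is using a wrong retention threshold.** The protocol sets no numerical retention target. Whether oversight would judge follow-up against the 20% figure is conjecture, and the correction does not need a target.

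**What to change.** Keep 240 and replace the last sentence of section 6.1 with one of these:

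- *A total of 240 randomised patients allows for about 17% (16.7%) loss to follow-up while keeping 100 evaluable patients per group and 90% power.*
- *With 20% loss to follow-up, 240 randomised patients leave 192 evaluable (96 per group) and about 89% power for a difference of 12 points with an SD of 26.*

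Either costs one sentence, changes no procedure, and makes the stated position slightly less favourable. The second keeps the 20% planning figure and states its consequence directly.

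If the sponsor prefers to keep both 20% loss and 90% power, the figure is 250, and section 2.1 would have to change as well. Section 7.5 projects 243.6 recruits at 8.4 per month, so the further 250 − 243.6 = 6.4 patients would take about one more month (6.4/8.4 = 0.8). The size of the error does not require this.

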6.2 Statistical Analysis Plan

It seems likely that some data may not be available due to voluntary withdrawal of participants, lack of completion of individual data items or general loss to follow-up. Where possible the reasons for data 'missingness' will be ascertained and reported. Although missing data is not expected to be a problem for this study, the nature and pattern of the missingness will be carefully considered, including in particular whether data can be treated as missing completely at random or missing at random. If judged appropriate, missing data will be imputed using the multiple imputation facilities (mice package) available in R (<http://www.r-project.org/>). The resulting imputed datasets will be analysed and reported, together with appropriate sensitivity analyses. Any imputation methods used for scores and other derived variables will be carefully considered and justified. Reasons for ineligibility, non-compliance, withdrawal or other protocol violations will be stated and any patterns summarized. More formal analysis, for example using logistic regression with 'protocol violation' as a response, may also be appropriate and aid interpretation.

Standard statistical summaries (e.g. medians and ranges or means and variances, dependent on the assumed distribution of the outcome) and graphical plots showing correlations will be presented for the primary outcome measure and all secondary outcome measures. Baseline data will be summarised to check comparability between treatment arms, and to highlight any characteristic differences between those individuals in the study, those ineligible, and those eligible but withholding consent.

The main analysis will investigate differences in the primary outcome measure, the VISA A at six months after treatment, between the two treatment groups on an intention-to-treat basis. In addition, early functional status will also be assessed and reported at three months. The differences between treatment groups will be assessed using a Student t-test, based on a normal approximation for the VISA A score at 6 months, and at other occasions. Tests will be two-sided and considered to provide evidence for a significant difference if p-values are less than 0.05 (5% significance level). Estimates of treatment effects will be presented with 95% confidence intervals.

The stratified randomisation procedure will ensure a balance in recruiting centres between test treatments. In addition to the unadjusted analysis (t-tests) we will also undertake regression analyses to adjust for any imbalance between test treatment groups in patient age or gender. The fixed effects analysis (linear regression model) will also be generalized by adding a random effect for recruiting centre to allow for possible heterogeneity in patient outcomes due more generally to the recruiting centre. VISA-A data will be assumed to be normally distributed during modelling, but subsidiary analyses may also be undertaken after appropriate variance-stabilizing transformation. The primary focus will be the comparison of the two treatment groups of patients, and this will be reflected in the analysis which will be reported together with appropriate diagnostic plots that check the underlying model assumptions. Treatment effects will be presented, with appropriate 95% confidence intervals, for both the unadjusted and adjusted analyses.

Temporal patterns of any complications will be presented graphically and if appropriate a time-to-event analysis (Kaplan-Meier survival analysis) will be used to assess the overall risk and risk within individual classes of important complications (e.g. infection). The decision about whether to undertake a time-to-event analysis will be data dependent; that is it will be dependent on the number of complications reported by study participants. The independent Data Monitoring and Ethics Committee will advise on this and suggest appropriate modifications to the statistical analysis plan as data is accumulated.

From the pilot data two patients from a sample of twenty presented with bilateral Achilles tendinopathy. For the full trial this small group will be randomised and treated as one unit i.e. the patient will be randomised rather than the tendon. Therefore, study participants presenting with bilateral tendinopathy will receive the same treatment on both sides. One side will be randomly selected, and designated as the index Achilles tendon. For those outcome measures (complications) that are side specific, we will use data from the index side only in the analysis. Randomisation will ensure approximate balance in bilaterals between groups; however, bilaterality will also be adjusted for in the definitive analysis. This will be incorporated into the Statistical Analysis Plan.

The detailed statistical analysis plan will be agreed with the Data Monitoring and Ethics Committee at the start of the study. Any subsequent amendments to this initial statistical analysis plan will be clearly stated and justified. Interim analyses will be performed only where directed by the Data Monitoring and Ethics Committee. The routine statistical analysis will mainly be carried out using R (<http://www.r-project.org/>). Results from this trial will also be compared with results from other trials.

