2.6.2.1 Post-randomisation withdrawals and exclusions

Participants may be discontinued from the trial treatment and/or the trial at any time without prejudice. Unless a participant explicitly withdraws their consent, they should be followed-up wherever possible and data collected as per the protocol until the end of the trial. For participants explicitly withdrawing consent for follow up procedures, trial data obtained up until the point of withdrawal will be included in the final analysis of the study. Participants will have the option to withdraw from the trial-related questionnaires, but continue to provide routine NHS data for the purposes of the trial e.g. hospital records of subsequent treatment for the Achilles condition.

Participants who withdraw will not be replaced in the trial and a corresponding CRF will be completed by the Trial Coordinator (TC).

All of the outcome questionnaires can be completed over the phone, or in the follow-up clinic, if postal copies are not returned. Text messages may be sent to participants to inform them that a questionnaire is due or on its way. Text messages will only be sent to those participants who have given their prior consent to this by initialling the corresponding box on the consent form. Text messages will be sent via the WCTU mobile phone from a secure office.

Participants may be withdrawn from the trial at the discretion of the investigator and/or Trial Steering Committee due to safety concerns **Trial treatments**

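### Section 6.2 names a six-month t-test that cannot use patients without a six-month score, leaves imputation discretionary, and does not say which estimate is primary

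*Protocol*

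**What the plan says.** The main comparison in section 6.2 is six-month VISA-A by allocated group. The difference "will be assessed using a Student t-test, based on a normal approximation for the VISA A score at 6 months", and the same section later calls the t-tests the unadjusted analysis. Further regression models bring in age, gender, bilaterality and a random centre effect. None is described as using baseline or three-month VISA-A.

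On missing data, section 6.2 accepts that some will be unavailable, adds "Although missing data is not expected to be a problem for this study", and says that the nature and pattern of missingness will be examined. Then: "If judged appropriate, missing data will be imputed using the multiple imputation facilities (mice package) available in R". Imputed datasets, if made, are to be analysed and reported with sensitivity analyses. No sentence ranks the imputed estimate against the t-test on observed scores.

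Two other places bear on this. Section 6.1 sets the margin: "Allowing approximately 20% loss to follow-up, this amounts to 240 patients in total". Section 2.6.2.1 says of patients who withdraw consent for follow-up that "trial data obtained up until the point of withdrawal will be included in the final analysis of the study". Sections 2.3.1 and 3.1 schedule VISA-A at baseline, three months and six months.

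**The concern.** A t-test on the six-month score needs a six-month score. Unless imputation is invoked, a patient who gave baseline and three-month VISA-A and was then lost has no weight in the primary estimate. The protocol therefore leaves two candidate primary estimates, and which one governs turns on a judgement that can be made only once missingness has been observed. Observed data cannot fully settle whether scores are missing at random, so that judgement has no firm end point.

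The completer difference is unbiased only if loss distorts the two arm means equally. In a painful condition with a placebo arm, patients may drop out according to how they are doing at three months, and may do so differently by arm. The three-month score, which carries information on this, is collected but not used in the named test.

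**Working it through.** **Inputs from the protocol.** Target difference 12 points, SD 26, 100 per group for 90% power, 240 in total with about 20% loss (6.1); two-sided 5% test (6.1, 6.2); 1:1 allocation (2.1).

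**The plan's own figure.** With a standardised difference of 12/26 = 0.46, a two-sided 5% t-test and 90% power, the requirement is 99.6, so 100 per arm. This agrees with 6.1. The total follows as 200 × 1.2 = 240.

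**Patients outside the t-test.** 0.20 × 240 = 48 lost, leaving 192, or 96 per arm. SE of the difference = 26 × √(2/96) = 3.75; power at 12 points is 88.9%. If loss is 16.7%, 40 are lost, 100 per arm remain and power is 90%. The power cost is about one percentage point.

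**Bias of the completer difference.** The following are assumptions, not protocol figures: 20% loss in each arm; correlation ρ of 0.5 to 0.8 between three- and six-month scores; SD 26 at both times; loss in the placebo arm following a logistic model in the standardised three-month score, with slope b per SD; loss in the PRP arm random. The intercept is set so that 20% are lost. Let m be the mean standardised three-month score of the placebo patients who stay. Then

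bias (absolute) = ρ × 26 × m.

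| b (log-odds per SD) | m | ρ = 0.5 | ρ = 0.8 |
|---|---|---|---|
| 0.25 (weak) | 0.0495 | 0.64 | 1.03 |
| 0.5 (moderate) | 0.0962 | 1.25 | 2.00 |
| 1 (strong) | 0.1732 | 2.25 | 3.60 |

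For example, 0.8 × 26 × 0.1732 = 3.60 points. Simulation gives the same values to within about 0.1 point. As a share of the 12-point target, weak to moderate dependence gives 0.64/12 = 5% to 2.00/12 = 17%, and strong dependence gives 2.25/12 = 19% to 3.60/12 = 30%. If it is the poor responders on placebo who leave, the completer result understates any benefit of PRP; if the good responders leave, it overstates it.

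**Same dependence in both arms.** With no three-month difference between arms, m is equal in both and the bias is 0. With a 12-point three-month difference and b = 1, m is 0.199 in placebo and 0.147 in PRP, so bias = ρ × 26 × 0.051, about 0.7 points at ρ = 0.5 and 1.1 at ρ = 0.8.

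**A cruder check.** If the lost patients in one arm differ by 6 to 12 points from those observed, and those in the other arm do not differ, bias = 0.20 × 6 = 1.2 to 0.20 × 12 = 2.4 points.

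**Using the three-month score.** Under the same assumptions, regression on the three-month score leaves a simulated bias within about 0.06 points of zero. For precision, the variance of an arm mean is 26² × [(1 − ρ²)/96 + ρ²/(96 + k)], where k is the number lost per arm who have a three-month score. For k = 12 to 24 and ρ = 0.5 to 0.8, the SE of the difference is 3.70 to 3.50, equivalent to 99 to 110 completers per arm, with power of 90% to 93%.

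**The case against.** Four stronger readings are tempting, and the protocol does not support them.

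- *That 6.2 contradicts 6.1.* A recruitment margin that protects power is compatible with not expecting serious harm from missing data, and the remark in 6.2 sits inside an explicit missing-data plan.
- *That the t-test breaks the promise in 2.6.2.1.* That section speaks of the final analysis of the study, not of the primary test. A later withdrawer's three-month score still enters the three-month comparison.
- *That it conflicts with the intention-to-treat label.* This depends on a definition that the protocol does not give. Analysis by allocated arm and handling of missing outcomes are separate matters.
- *That imputation is decided with results in view.* The text ties the judgement to the pattern of missingness and does not say that allocation or treatment results are known when it is made.

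Other points also carry weight. Blinded participants make a sharp difference in loss by arm less likely, though they do not exclude it. Phone and clinic completion of questionnaires (2.6.2.1) should reduce loss. The strong-dependence figures are the severe end of the range. The t-test could be pooled over imputed datasets. A detailed plan is to be agreed at the start of the study and may settle the method.

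What remains is what 6.2 itself fixes: a named main test that omits patients without the six-month score, a discretionary alternative, and no ranking between them. If the separate plan does settle this, 6.2 still has to agree with it.

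**Conclusion.** The point holds as a choice of primary analysis that can be improved, not as a contradiction in the protocol. As written, up to about 48 of 240 patients contribute to the primary six-month estimate only if imputation is later judged appropriate.

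The consequence for bias ranges from nothing to 3.6 points on a 12-point target, depending mainly on how far loss follows early response and how much that differs by arm. The protocol gives no figure for either, nor for the three-to-six-month correlation, so the range is illustrative. The loss of power is minor. A model using the three-month score removes the bias only if data are missing at random given the observed scores.

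**What to change.** In 6.2, name one primary six-month analysis that uses the VISA-A already collected: a linear mixed model on three- and six-month VISA-A with baseline VISA-A, treatment-by-time, and the stratification factors (centre and bilateral symptoms). The six-month treatment contrast is the primary estimate. Multiple imputation that always includes baseline and three-month VISA-A by arm would serve as well, provided it is stated as the rule and not as an option. Keep the t-test on observed six-month scores as a supportive analysis. Sensitivity analyses for departures from missing at random can stay with the separate statistical analysis plan.

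The cost is a change of wording and modest analysis work; no new data are needed and the sample size stands. The downside is a slightly more complex main model that assumes missing at random given the observed scores.

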2. TRIAL DESIGN

2.1 Trial summary and flow diagram

This will be a single blinded, multi-centre, randomised placebo controlled trial. The considered opinion of the Arthritis Research UK CSG Think Tank – which included representatives from rheumatology, podiatry, orthopaedics, physiotherapy, general practice and research – was that in the non-athletic population there is very limited evidence of the effectiveness of eccentric loading exercises, or indeed any other intervention, for this condition. It was the considered opinion of the Think Tank that there was no ‘standard treatment’ for the general population. Therefore, the

pivotal and crucial trial design which is likely to influence clinical practice should involve a placebo-arm.

[figure not shown]
All patients who are willing to proceed will be approached by a suitably qualified member of the research team who are responsible for completing consent procedures and baseline demographic data and functional outcomes using VISA-A and EQ-5D-5L **before randomisation**. The patient will be randomised using a centralised telephone randomisation service to either the intervention or the placebo injection, on a 1:1 basis, stratified by centre and presence of bilateral symptoms. **After randomisation**, the suitably qualified member of the research team will then prepare the allocated injection for the principal investigator who will administer the injection. The participant will not know the treatment allocation.

Two hundred and forty patients will be randomised in total, across six participating centres. The intervention delivery will be standardised through initial training and on-going quality assurance checks by an independent researcher. The participants will then attend routine clinical appointments, (typically two weeks post injection to assess for any adverse events and six months post injection to review treatment efficacy). The participants will also receive two postal follow up questionnaires, as part of research procedures, at three and six months following randomisation.

The local principal investigator and research team at each site cannot be blind to treatment as they will be delivering the interventions. None of these team members will have a role in the collection of participant data after randomisation or analysis, beyond reporting adverse events.

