2.6.2 Randomisation

Pre-randomisation eligibility checks will be carried out to ensure that patients meet the eligibility criteria and are not randomised in error. Written informed consent for entry into the trial must be obtained prior to randomisation. Subjects will be randomised strictly sequentially, as they become eligible for randomisation.

The treatment group will be allocated using a secure, centralised, telephone-based randomisation service. The randomisation service will be available Monday-Friday, 9am-5pm each day to facilitate the inclusion of all eligible patients. The allocated treatment will be reported to a member of the research team who will prepare the treatment allocation and inform the PI. The PI will then administer the treatment allocation, however the allocation will remain concealed from the

participant. A sticker will be placed on participants clinical notes for flagging their inclusion in the trial.

Stratification by centre will help ensure that any clustering effect related to the centre itself will be equally distributed in the trial arms. The catchment area (the local population served by the hospital) will be similar for all of the hospitals; each hospital delivering a specialist foot and ankle clinic. Stratification based on bilateral presentation will also be implemented to account for the poorer outcome associated with this sub population.

Details of the WCTU randomisation service are below:

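### The main six-month comparison is an unadjusted t-test, an undefined definitive analysis adjusts for bilaterality, and baseline VISA-A is in no named model: precision and clarity are given up at no saving

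*Protocol*

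**What the plan says.** Protocol section 6.2 sets the main analysis as an intention-to-treat comparison of VISA-A at six months. The method is "The differences between treatment groups will be assessed using a Student t-test, based on a normal approximation for the VISA A score", and the same test is used at the other time point. The decision rule is also given there: "Tests will be two-sided and considered to provide evidence for a significant difference if p-values are less than 0.05".

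Section 6.2 then adds further analyses. Alongside the t-tests there will be "regression analyses to adjust for any imbalance between test treatment groups in patient age or gender", and this model will be extended with a random effect for recruiting centre. Effects with 95% confidence intervals will be shown for both the unadjusted and the adjusted analyses. Later in the section, on bilateral disease, it says that "bilaterality will also be adjusted for in the definitive analysis", and that this will go into the SAP. The definitive analysis is not defined and is not placed in order against the t-test.

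Two facts from the design bear on this. Section 2.1 has patients randomised 1:1, "stratified by centre and presence of bilateral symptoms"; section 2.6.2 explains that bilaterality was chosen "to account for the poorer outcome associated with this sub population". Sections 2.1 and 2.3.1 have every participant complete "functional outcomes using VISA-A and EQ-5D-5L" before randomisation. Baseline VISA-A is not named as a covariate anywhere.

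**The concern.** There are two issues, and one edit settles both.

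**Which analysis is primary.** A two-sample t-test cannot adjust for bilaterality, so the main analysis and the definitive analysis cannot be the same calculation. The protocol has one 5% threshold and two estimates that could be judged against it.

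**Precision.** The baseline score on the outcome scale is the natural candidate for explaining variation in the six-month score. It is collected anyway, so leaving it out saves nothing. The t-test also omits the two factors on which randomisation is balanced, one of which the protocol itself regards as prognostic. When balanced prognostic factors are left out, the usual standard error is somewhat larger than the true sampling variation of the estimate, so the intervals are a little too wide.

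A lesser point is that age and gender are to be adjusted for because of imbalance. This reads as if the covariates depend on what is observed.

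**Working it through.** **Inputs from the protocol.** Section 6.1: difference 12, SD 26, power 90%, significance level 5%, 100 per arm, about 20% loss, 240 in total. Section 6.2: two-sided tests; 2 of 20 pilot patients bilateral (10%).

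**Assumed inputs.** The within-arm correlation r between baseline and six-month VISA-A is not in the protocol; 0.2 to 0.6 is used. The share of outcome variance explained by the strata is not given either; 2% to 10% is used. So is a deficit of 5 to 20 points for bilateral patients.

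**1. The plan's own figure.** By the normal approximation, n per arm = 2(1.960 + 1.282)² × 26² / 12² = 98.7, rounded up to 99. The noncentral t calculation gives 99.6, rounded up to 100. Power at 100 per arm is 0.901. The stated size is reproduced, and it is the size for an unadjusted test.

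**2. Completers.** 240 × 0.80 = 192, or 96 per arm. T-test power is then 0.889. The small gap below 90% arises because 240 is 200 × 1.2 and not 200 / 0.8 = 250; it is not due to the choice of test.

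**3. Adding baseline VISA-A.** Residual SD = 26√(1 − r²). Standard error = residual SD × √(2/96). Half-width = 1.9725 × standard error (t quantile on 190 degrees of freedom; the few degrees of freedom spent on covariates are ignored).

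| r (assumed) | Residual SD | Standard error | 95% CI half-width | Power at difference 12 |
|---|---|---|---|---|
| t-test | 26.0 | 3.75 | 7.40 | 0.889 |
| 0.2 | 25.5 | 3.68 | 7.25 | 0.901 |
| 0.3 | 24.8 | 3.58 | 7.06 | 0.915 |
| 0.5 | 22.5 | 3.25 | 6.41 | 0.957 |
| 0.6 | 20.8 | 3.00 | 5.92 | 0.978 |

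The variance removed is r²: 9% at r = 0.3, 25% at 0.5 and 36% at 0.6. The half-width is also the smallest estimate that reaches p < 0.05. At r = 0.5, an estimate of 7 points would be non-significant on the t-test's standard error (7 < 7.40) and significant on the adjusted one (7 > 6.41). So the ranking of the two analyses can matter to the conclusion.

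**4. How much comes from bilaterality.** With prevalence 0.10 and a deficit of D points, the share of variance is 0.10 × 0.90 × D² / 26². For D = 5 this is 2.25 / 676 = 0.3%; for D = 20 it is 36 / 676 = 5.3%. Even the larger value only brings the half-width to 7.40 × √(1 − 0.053) = 7.20. Nearly all the gain to be had comes from baseline VISA-A.

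**5. The t-test after stratified randomisation.** If well-balanced strata explain a share R² of the variance, the actual two-sided error is about 2[1 − Φ(1.96 / √(1 − R²))]. For R² = 0.02, 0.05 and 0.10 this is 4.8%, 4.4% and 3.9%. The departure is always on the conservative side.

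**The case against.** The strongest reply is that nothing in the planned test is wrong. The unadjusted estimate is unbiased over the randomisation, its interval already allows for chance baseline imbalance, its type I error is at or slightly below 5%, and the sample size was calculated for it. All of this stands. A reader might infer from an unadjusted main analysis that the trial is biased or underpowered; step 1 shows that the protocol's figures do not support that.

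A reader might also infer that the stratification factors are ignored altogether. They are not. Section 6.2 puts centre into an additional model as a random effect and promises adjustment for bilaterality. Only baseline VISA-A is absent from every named model.

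Next, the two statements have an ordinary reading: an unadjusted t-test, plus an adjusted regression that also includes bilaterality. Section 6.2 has the detailed SAP agreed with the data monitoring committee at the start of the study, with later amendments stated and justified; section 7.9 likewise places agreement at the commencement of the trial. Both results will be reported. So the stronger inference, that the headline p-value is open to choice once the data are seen, is not supported: there is a stated prospective control. What remains is that the protocol itself fixes a t-test for the main analysis and calls a different analysis definitive. That ambiguity is in the text and does not depend on what the SAP, which is not at hand, may contain.

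Last, the size of the gain rests on r, which nothing in the protocol supplies. At r = 0.3 it is 2.6 percentage points of power and about 0.3 points of half-width. That is a fair caution, and the reason for giving a range.

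**Conclusion.** The point holds as a free improvement and a needed clarification; it is not a defect that invalidates the plan. The protocol leaves it unclear whether the t-test or the bilaterality-adjusted analysis is primary, and it uses baseline VISA-A in no named analysis.

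At 96 completers per arm, SD 26 and a true difference of 12, adjustment for baseline would take power from 88.9% to between 91.5% (r = 0.3) and 97.8% (r = 0.6), and the half-width from 7.4 to between 7.1 and 5.9 points. Even r = 0.2 restores power to about 90%. These figures are conditional on the assumed r and on a roughly linear relation between the baseline and six-month scores. The mild conservatism of the t-test (actual error about 4.8% to 3.9%) is conditional on the strata explaining an assumed 2% to 10% of the variance.

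**What to change.** In section 6.2, name one primary analysis: a prespecified linear (or mixed) model of six-month VISA-A on treatment, baseline VISA-A, bilaterality and centre. Include age and gender, if wanted, by prior choice and not because an imbalance was observed. Keep the t-test as a supporting unadjusted analysis. Reword the sentence on the definitive analysis so that it refers to this model, and carry the same ranking into the SAP.

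The cost is wording in the protocol and SAP. Baseline VISA-A, centre and bilaterality are already collected, so no new data are needed. The sample size can stay as it is, since it was set for the less precise test.
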